2. OBJECTIVES

Primary Objective: The primary objective of the Girls United cluster Randomized Controlled Trial (cRCT) is to examine the effectiveness of the Girls United prevention program on self-reported co-rumination.

Secondary Objectives: The second objective of this study is to investigate the intended active mechanisms of this program, especially enhancement of mindfulness and emotion regulation skills. Furthermore, the effectiveness of the Girls United mindfulness-based prevention program on self-reported symptoms of depression and anxiety, self-reported contagion of depression and anxiety symptoms, self- and friend-reported friendship quality, self-reported positive and negative affect, interpersonal responses to positive affect, self-reported self-worth

and parent-reported health care use will be studied in Dutch young adolescent girls from age 10 to 12 years old.

The research question is: To what extent does the app-based mindfulness prevention program Happy Friends, Positive Minds impact mental health and well-being in Dutch 10-to-12-year-old girls?

Hypotheses:

- (1) Girls in the intervention group will have a greater reduction in co-rumination (primary outcome) about distress and difficult emotions and feelings, (and thereby) internalizing symptoms (depression/anxiety, secondary outcome) and negative affect (secondary outcomes) during the intervention period, immediately after the intervention period and after one-year follow-up, relative to girls in the control condition.
- (2) Girls in the intervention group will have less dyadic depression contagion, immediately after the intervention period and after one-year follow-up, relative to girls in the control condition.
- (3) Girls in the intervention group will demonstrate less dyadic anxiety contagion during the intervention period, immediately after the intervention period and after one-year follow-up, relative to girls in the control condition.
- (4) Girls in the intervention group will experience better friendship quality, higher levels of positive affect and higher levels of interpersonal responses to positive affect, during the intervention period, immediately after the intervention period and after one-year follow-up, relative to girls in the control condition.

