Self-reported positive and negative affect will be assessed using the Dutch version of the Positive and Negative Affect Schedule for Children (PANAS-C; Laurent et al., 1999; De Bolle, De Fruyt & Decuyper, 2010). The PANAS-C includes two subscales: Positive Affect (15 items, e.g., energetic) and Negative Affect (15 items, e.g., nervous). Participants will be asked to indicate how often they have experienced each feeling over the past few weeks, using a scale from 1 (very slightly or not at all) to 5 (extremely). The internal reliability of the Dutch version was found to be moderate to good, with Cronbach's α ranging from 0.66 to 0.83 for the Positive Affect subscale and 0.67 to 0.81 for the Negative Affect subscale. Additionally, a dummy variable will be created to represent the type of day (0 = weekend, 1 = weekday). To account for the time of day, separate dummy variables will be created to indicate whether the assessment occurred in the morning (1 = morning, 0 = afternoon and evening), afternoon (1 = afternoon, 0 = morning and evening), or evening (1 = evening, 0 = morning and afternoon).

Self-reported interpersonal responses to positive affect

Self-reported interpersonal responses to positive affect will be measured using the Co-Dampening and Co-Enhancing Questionnaire (CoDEQ; Bastin, Nelis, Raes, & Bijttebier, 2018). The questionnaire consists of 18 items, with nine items measuring co-enhancing responses and nine items measuring co-dampening responses to positive feelings within dyads. Co-dampening responses describe reactions such as thinking about the fleeting nature of positivity, focusing on worries, emphasizing negative aspects of a positive event, making upward social comparisons (e.g., considering how others are better off), making external attributions (e.g., attributing success to luck), and reflecting on past negative events. In

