contrast, co-enhancing items focus on positive reactions, including behavioral displays, focusing on positive feelings (e.g., thinking about how energetic one feels), thinking about positive past or future events, making downward social comparisons (e.g., comparing oneself to others who are less fortunate), and recognizing positive personal qualities (e.g., believing in one's ability to achieve goals). Respondents will indicate how often they respond in these ways when they or their friend feel happy and discuss it. The rating scale has four response options: almost never (1), sometimes (2), often (3), and almost always (4). The Cronbach's alphas for co-enhancing and co-dampening were 0.84 and 0.86, respectively.

Self-reported quality of the friendship with the dyad friend and investments in the interpersonal relation

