Self-reported support quality of the friendship with the dyadic friend and investments in the interpersonal relationship will be measured using the Dutch version of the Network of Relationships Inventory (NRI; Furman & Buhrmester, 1992), which includes 36 items across seven subscales. The subscale Support consists of eight items. Girls and their best friend were instructed to take each other in mind while answering items such as: "How much does your best friend really care about you?". The subscale Relative Power consists of six items ("To what extent is your friend the boss in your relationship?"). The subscale Negative Interaction consists of six items ("Are you and your friend annoyed by each other's behavior?"). The subscale Seeks Safe Haven consists of three items ("To what extent do you visit your friend when you are upset?"). The subscale Provides Safe Haven consists of three items ("To what extent does your friend visit you when she is worried about something?"). The subscale Seeks Secure Base consists of three items ("To what extent does your friend support you in the things you do?"). Finally, the subscale Provides Secure Base consists of three items ("To what extent do you support your friend in the things she does?"). Responses will be rated on a 5-point Likert scale 0 (little or none) to 4 (the most). The English version of the NRI shows good psychometric properties in adolescent samples, such as high internal consistency and moderately high stability over a 1-year period (Furman & Buhrmester, 2009). Furthermore, in a Dutch sample that used a shorter version of the NRI friend-scales, it was shown that the internal consistencies were high for all variables (Cronbach's alpha range $\alpha = 0.82-0.93$) and that the factor and construct validity of the NRI are adequate (De Goede et al., 2009).

Self-reported self-worth

Self-reported self-worth will be measured with the original Dutch version of the Competentie-Beleving Schaal voor Kinderen (CBSK; Veerman, Straathof & Treffers, 1994) and is intended to measure self-worth in children between 8 and 12 years old. It assesses children's perceived competence and self-value, offering insights into their self-esteem and overall self-concept. It

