Hypothesis 4 “Girls in the intervention group will experience better friendship quality, higher levels of positive affect and higher levels of interpersonal responses to positive affect during the intervention period, immediately after the intervention period and after one-year follow-up, relative to girls in the control condition” will be tested using multi-level LGMs for each outcome, respectively.

Three multi-level LGMs with intervention arm as the exogenous predictor variable and growth rate of friendship quality, positive affect and interpersonal responses to positive affect as the (potentially correlated) outcome variables, will be used to test whether girls in the intervention arm experience more improvements in friendship quality, a faster growth in positive affect and faster growth levels of interpersonal responses to positive affect, compared to girls in the control arm. The outcome variables will be modelled on both the individual (within) level and

on the dyadic (between) level. This way, the between-level intervention effects will be adjusted for variation between individuals in the outcome measures on the within-level. Note that we have no a priori hypotheses regarding the nature of the growth patterns of the outcome measures and that it may best be captured by either a linear or a non-linear slope. We will adjust the analysis accordingly.

Hypothesis 5 “The hypothesized intervention effects on co-rumination (primary outcome) will be mediated by the development of mindfulness and emotion regulation skills during the intervention period, immediately after the intervention period and after one-year follow-up” will be tested using a multi-level parallel process LGMs for self-reported co-rumination.

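### Hypothesis 4 predicts higher interpersonal responses to positive affect as one outcome, but the CoDEQ has two opposing subscales, so the stated direction is wrong for co-dampening and its reduction is never tested

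*Protocol*

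**What the plan says.** Section 2 of the protocol, Hypothesis 4, predicts "higher levels of interpersonal responses to positive affect, during the intervention period" and at the later time points, relative to control. No subscale is named. Section 10.2 carries this into the analysis. It sets three multi-level latent growth models for friendship quality, positive affect and interpersonal responses, with intervention arm as predictor, and looks for "faster growth in positive affect and faster growth levels of interpersonal responses to positive affect".

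Section 8.1.2 names the CoDEQ as the measure: "The questionnaire consists of 18 items, with nine items measuring co-enhancing responses and nine items measuring co-dampening responses to positive feelings within dyads". Co-dampening covers reactions such as "focusing on worries, emphasizing negative aspects of a positive event". By contrast, "co-enhancing items focus on positive reactions, including behavioral displays, focusing on positive feelings". Every item is rated for frequency on a scale from 1 to 4, and no item is said to be reverse-scored. Cronbach's alpha is reported per subscale (0.84 for co-enhancing, 0.86 for co-dampening). No total or difference score is described.

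**The concern.** The two halves of the CoDEQ describe opposite ways of responding when a friend is happy. A programme that trains girls to appreciate pleasant shared experiences and to notice when they dwell on negative emotions together (section 5.1) should raise one half and lower the other. The hypothesis gives a single direction, upward, for the whole construct. For co-dampening that is the unfavourable direction.

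Two things are at stake. First, the criterion for success does not match the instrument: a rise in co-dampening fits the wording of Hypothesis 4, and a fall, which would be a benefit, has no hypothesis and no test. Second, because the subscale is not named, the choice between co-enhancing, co-dampening and some combination stays open until the data are in, when it can be swayed by the results.

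**Working it through.** The protocol gives no figure for the CoDEQ, so there is none to reproduce. The check sets the sections side by side and then adds a conditional illustration.

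**1. Comparison with the PANAS-C.** Section 8.1.2 describes another instrument with two opposing subscales, and the hypotheses treat it differently.

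| Instrument | Favourable scale | Unfavourable scale |
|---|---|---|
| PANAS-C | Positive affect: predicted higher (Hypothesis 4) | Negative affect: predicted to fall (Hypothesis 1) |
| CoDEQ | Co-enhancing: not named | Co-dampening: not named; the whole construct is predicted higher |

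**2. Possible readings of section 10.2.**
- *One score from all 18 items.* The model count fits, but no reversal is stated, so half the items push the score the wrong way.
- *Two subscale scores.* The separate alphas suggest this. Then three models do not cover the outcomes (friendship quality, positive affect, co-enhancing and co-dampening make four), and the upward direction is wrong for one of them.
- *Co-enhancing only.* The direction fits, but the text does not say so, and co-dampening is collected throughout without a hypothesis or an analysis.

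None of the three gives co-dampening a correctly directed test.

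**3. Illustration, conditional on the first reading.** Let the effects on co-enhancing and co-dampening be dE and dD in SD units, with equal SDs and subscale correlation r. The standardised effect on the un-reversed sum is

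(dE + dD) / sqrt(2 + 2r).

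The documents give neither r nor CoDEQ effects. Assumed: r from -0.3 to +0.3, and effects of 0.5 SD (the planning value in section 4.4, which is not specific to this instrument).

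- Benefit on both (+0.5, -0.5): 0 / sqrt(2 + 2r) = 0 for any r.
- Benefit on co-enhancing only (+0.5, 0): 0.5 / sqrt(1.4) = 0.42 at r = -0.3; 0.5 / sqrt(2) = 0.35 at r = 0; 0.5 / sqrt(2.6) = 0.31 at r = +0.3.
- Harm on co-dampening only (0, +0.5): the same 0.31 to 0.42, in the direction that Hypothesis 4 calls success.

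**4. What this means for detection, same condition.** Inputs from sections 4.4 and 8.2: 122 dyads allocated 1:1 (61 per arm), within-dyad ICC 0.40, alpha 0.05 (two-sided assumed). For a simple comparison of dyad means, SE = sqrt((1 + 0.40)/2) x sqrt(2/61) = 0.837 x 0.181 = 0.151 SD.

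- One subscale tested alone, 0.5 SD: 0.5 / 0.151 = 3.30, and power = Phi(3.30 - 1.96) = 0.91. With 160 dyads it is 0.97.
- Un-reversed sum, benefit on co-enhancing only: power 0.54 to 0.80 over the same range of r.
- Un-reversed sum, equal and opposite benefits: 0.025 chance of a significant result in the predicted direction.

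This formula is not the protocol's own calculation, which used repeated measures and further inputs not shown. It serves only to compare scorings.

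**The case against.** The strongest reply is that the protocol never plans an 18-item total. It presents two scales, contrasts them and reports reliability for each. Section 10.2 names constructs rather than scales throughout: Hypothesis 6 has one self-worth model although the CBSK has six subscales, and Hypothesis 5 names mindfulness without choosing between the MAAS-A and the CAMM. On that convention, the count of three models says little about scoring, which may be left to a statistical analysis plan. In context, the phrase may simply be loose shorthand for co-enhancing.

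Much of this stands. A reader might infer that the planned analysis will cancel a true benefit or credit harm as success. The documents do not support that: the un-reversed total is neither stated nor ruled out, and the figures above also rest on assumed effects, SDs and correlations.

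A reader might also extend the point to friendship quality, because the NRI combines Support with scales such as Negative Interaction. That does not hold. Hypothesis 4 says that friendship quality will be better, which is an evaluative term and gives no wrong direction for any subscale. Section 8.1.2 also introduces the measure as support quality.

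The reply does not remove the mismatch in direction. The hypothesis and its direction are fixed in this protocol, in two sections, and they conflict with the instrument as the protocol describes it. An analysis plan that predicted lower co-dampening would depart from the stated hypothesis rather than fill in a detail.

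**Conclusion.** The point holds for the CoDEQ. The upward direction in Hypothesis 4 is wrong for co-dampening. Taken literally, more co-dampening would support the hypothesis, and no stated analysis tests for its reduction. This follows from the text alone and needs no assumption about scoring.

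The size of any distortion is conditional. Only if one un-reversed 18-item score were used would opposing effects offset each other: fully when they are equal and opposite with equal SDs, and from 0.5 SD down to 0.31 to 0.42 SD when co-enhancing alone improves, for an assumed r of +0.3 to -0.3.

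One secondary outcome is affected. The primary outcome, co-rumination, is not. The correction should be made before outcome data are analysed, but it does not threaten the trial's main conclusion.

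**What to change.** Restate Hypothesis 4 in sections 2 and 10.2 so that it predicts higher co-enhancing and lower co-dampening. In section 10.2, specify a separate multi-level growth model for each CoDEQ subscale, which makes four models for Hypothesis 4 instead of three.

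The cost is a change of wording in two sections and one additional secondary test. No further data are needed, because the full CoDEQ is already scheduled in section 8.1.2 from T0 to T5.

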4.4 Sample size calculation

Multi-level models are used with individuals nested in dyads. To determine the required sample size for this cRCT study power analyses were conducted using Optimal Design Plus – Evidence (Raudenbusch, 2011). These analyses were based on an alpha level (α) of .05, with three measurement points (baseline and two follow-up measurements), and an intraclass correlation (ICC) of .40 between two friends (ρ). This ICC was derived from observed ICCs for perceived support within friendship dyads ($n = 266$ pairs) in an existing dataset of adolescents with an average age of 13. For average risk girls (M), the multilevel power analysis was based on an expected effect size (Cohen's d) of 0.50, indicating a small to medium effect. The power analysis showed that, to achieve a power level of 0.80, at least 122 average-risk friendship dyads would need to be included. However, we will aim to oversample to a maximum of 160 dyads in order to be able to compensate for loss to follow up .

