10. STATISTICAL ANALYSIS

10.1 Primary study parameter(s)

To test the primary hypothesis, the following statistical analyses will be conducted:

Hypothesis 1 “Girls in the intervention group will have a greater reduction in co-rumination (primary outcome) about distress and difficult emotions and feelings, (and thereby) internalizing symptoms (depression/anxiety, secondary outcomes) and negative affect (secondary outcome) during the intervention period, immediately after the intervention period and after one-year follow-up, relative to girls in the control condition” will be tested via a multi-level (within level = girls within dyads; between level = dyads) parallel process, dual latent growth curve model (with co-rumination measured via self-report).

For analysis with co-rumination measured via self-report (T0 to one-year follow up T5), we will use multi-level parallel process, dual latent growth curve (LGM) models, with intervention arm as the exogenous predictor variable, growth rate of co-rumination (primary outcome) as the mediating variable and growth rate of internalizing symptoms as (correlated) secondary outcome variables. The mediator and primary and secondary outcome variables will be

modelled on both the individual (within) level and on the dyadic (between) level. This way, the between-level intervention effects will be adjusted for variation between individuals in co-rumination (primary outcome) and internalizing symptoms (depression/anxiety, secondary outcomes) at the within-level. Note that we have no a priori hypotheses regarding the nature of the growth patterns of the mediator and outcome variables and that they may be best captured by either a linear or a non-linear slope. We will adjust the analyses accordingly. For a (simplified) visual representation of this model, please see Figure 2. For a more technical description of this model, see Preacher, Zyphur, & Zhang, 2010; Preacher, Zhang, & Zyphur, 2011).

[figure not shown]

Figure 2. Simplified visual representation of a multilevel, duals process latent growth model with a predictor (e.g., intervention condition), mediator (e.g., co-rumination, primary outcome) and secondary outcomes (e.g., anxiety/depression). Ovals represent latent variables; squares represent observed variables. Double headed arrows represent (residual error) correlations, single headed arrows represent regression paths. Paths of interest are in bold.

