All analyses will be conducted in structural equation modeling program Mplus (v 8.7 or higher; Muthén and Muthén, 1998-2017). Model fit will be determined using the comparative fit index (CFI, critical value $\geq .95$), the root mean square error of approximation (RMSEA, critical value $\leq .06$) and the standardized root mean square residual (SRMR, critical value $< .08$; Hu & Bentler, 1999). When appropriate, standard errors will be adjusted for clustering of dyads within schools using a sandwich estimator (Williams, 2000). For hypotheses that include mediation analysis (hypothesis 1 & 5) we will use 10.000 bootstrap resamples with replacement and bias-corrected 95% confidence intervals to test these indirect effects (Preacher and Hayes, 2004). When appropriate, differences in (indirect) pathways between the intervention and the control arm will be estimated using the DIFFtest option in Mplus (when using the WLSMV estimator) or the Satorra Bentler chi-square difference test (Satorra & Bentler, 2001; when using the MLR estimator).

Handling of protocol non-adherence and missing data

The way the questionnaires are administered online makes it impossible to skip a question. Participants who do not complete a questionnaire will receive one or more reminders. Missing data during the follow-up period (e.g., due to unavailability during a certain measurement wave or due to dropout) will be handled using Full Information Maximum Likelihood (FIML) estimation.

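### The bootstrap test of the indirect effects (Hypotheses 1 and 5) does not say that whole dyads are resampled, and its bias-corrected interval is somewhat anti-conservative even if they are

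*Protocol*

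**What the plan says.** Section 8.2 of the protocol randomises dyads 1:1. If randomisation cannot be done on one day, it proceeds in batches of 50 dyads and at classroom level. Section 4.4 sizes the trial with "an intraclass correlation (ICC) of .40 between two friends". Section 10.1 tests Hypothesis 1 with a "multi-level (within level = girls within dyads; between level = dyads) parallel process, dual latent growth curve model", in which growth in co-rumination mediates between arm and growth in internalising symptoms. Section 10.2 tests Hypothesis 5 with a model of the same kind, in which mindfulness and emotion regulation mediate the effect on co-rumination. Its variables are also modelled at girl and dyad level.

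Under the statistical software heading of Section 10.2, the indirect effects are tested as follows: "we will use 10.000 bootstrap resamples with replacement and bias-corrected 95% confidence intervals to test these indirect effects". The same paragraph says that, when appropriate, "standard errors will be adjusted for clustering of dyads within schools using a sandwich estimator". Nothing in Section 10 says whether girls or dyads are drawn in the bootstrap.

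**The concern.** In a trial randomised by dyad, the resampling unit decides whether a bootstrap interval is valid. If single girls are drawn, friends are separated and the path from arm to mediator is treated as if it rested on twice as many independent units as were randomised. The sandwich adjustment does not repair this. It addresses another level (dyads within schools) and it acts on standard errors, whereas a percentile or bias-corrected interval is read from quantiles of the resampled estimates.

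The bias-corrected interval raises a second, separate issue: it can reject too often when one of the two paths is zero, whatever unit is drawn.

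At stake are the mechanism claims. One is the part of Hypothesis 1 that attributes lower symptoms to reduced co-rumination. The other is Hypothesis 5, which corresponds to the second objective in Section 2. An arm that moves the mediator when the mediator does not drive the outcome is the false claim that such a test should prevent.

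**Working it through.** **Inputs from the protocol.** Alpha .05 (two-sided assumed, since no sidedness is given); ICC .40; 122 dyads required and 160 at most (Section 4.4); arm constant within a dyad (Section 8.2). The ICC is not from the variables tested here: "This ICC was derived from observed ICCs for perceived support within friendship dyads", at an average age of 13.

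**The plan's own sample size.** It states that "to achieve a power level of 0.80, at least 122 average-risk friendship dyads would need to be included", with d = 0.50. A simple two-group calculation gives 63 girls per arm. Then 2 × 63 × (1 + 0.40) = 176.4 girls, or about 88 dyads (90 with the noncentral F). So 122 is not reproduced, but the variance inputs of the three-wave calculation are not given, so it is not shown to be wrong. The present point does not depend on it.

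**Arm path if dyads are ignored.** With two girls per dyad, the true variance of an arm difference is (1 + ICC) times the variance assumed under independence. Hence

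actual alpha = 2 × [1 − Φ(1.96 / √(1 + ICC))].

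- ICC .40: 1.96 / √1.40 = 1.656, giving 9.8% (1.95 times 5%).
- ICC .20: 7.4%; .30: 8.6%; .50: 11.0%.
- Exact doubling needs an ICC of about .42.

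**Indirect effect, by simulation.** This uses a simplified stand-in for the growth model: one mediator, arm at dyad level, residual ICC .40 in mediator and outcome, and least-squares paths a (arm to mediator) and b (mediator to outcome). There were 3,000 trials per row and 1,000 resamples per trial, drawn across both arms. The path values are assumed. Entries are the percentage of trials in which the 95% interval excludes zero when the true product a × b is zero (BC = bias-corrected).

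| Dyads | a | b | Girls, BC | Girls, percentile | Dyads, BC | Dyads, percentile |
|---|---|---|---|---|---|---|
| 122 | 0 | 0.3 | 13.7 | 10.7 | 8.5 | 5.8 |
| 122 | 0 | 0.5 | 10.8 | 9.3 | 5.8 | 5.0 |
| 122 | 0 | 0.8 | 10.8 | 10.1 | 5.8 | 5.4 |
| 122 | 0.5 | 0 | 10.4 | 7.5 | 8.7 | 5.0 |
| 122 | 0 | 0 | 1.4 | 0.6 | 0.8 | 0.1 |
| 160 | 0 | 0.3 | 12.8 | 10.5 | 7.2 | 5.4 |
| 160 | 0 | 0.5 | 10.8 | 10.3 | 6.2 | 5.6 |
| 160 | 0 | 0.8 | 10.4 | 9.9 | 5.4 | 5.1 |
| 160 | 0.5 | 0 | 10.0 | 7.3 | 8.1 | 5.4 |
| 160 | 0 | 0 | 1.2 | 0.6 | 0.6 | 0.2 |

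Simulation error near 5% is √(0.05 × 0.95 / 3000) = 0.4 percentage points. A further simulation of the same design gave 9 to 13% with girls resampled and the stated interval, hence the overall range of 9 to 14%.

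**Lower ICC.** At ICC .20 with a = 0 and b = 0.5, girls resampled with the bias-corrected interval give 8.1% (122 dyads) and 8.4% (160 dyads), so about 8 to 9%.

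**Separating the two sources.** With the bias-corrected interval and one path non-zero, moving from dyads to girls multiplies the error by 1.2 (10.4 / 8.7) to 1.9 (10.4 / 5.4). With dyads resampled, the bias correction alone accounts for the difference between 5.4 to 8.7% and 5.0 to 5.8%.

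**The case against.** The strongest reply is that the text is silent on the unit. The bootstrap is named for models whose between level is the dyad, and resampling dyads fits that description at least as well as resampling girls. A statistical analysis plan, not shown here, may settle it. This stands. A reader might infer that the plan uses an ordinary bootstrap that ignores the dyads, but the protocol does not say so and describes no data layout or resampling procedure from which it would follow.

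A reader might also infer that the error rate at least doubles. That is not supported either. The closed form at ICC .40 is 1.95 times nominal and falls with the ICC. With both paths null the rate is about 1%, and compared with the dyad bootstrap the excess is 1.2 to 1.9 times.

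The ICC is borrowed and the simulation is not the planned latent growth model. Both are fair limits on precision. The bias-corrected interval is also a recognised method with slightly more power.

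What the reply does not remove is the result on its own preferred reading. With whole dyads drawn, the interval that the protocol fixes still rejects at up to 8.7%. The protocol already commits to the number of resamples and the type of interval, so this is a choice made in the text and not merely detail left for later.

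**Conclusion.** The point holds in a conditional form. The protocol fixes a bias-corrected bootstrap for the indirect effects without stating that the randomised unit is resampled, and the clustering adjustment beside it does not reach that interval. If girls were drawn, the 5% error rate would become roughly 9 to 14% at ICC .40 when one path is non-zero. If dyads are drawn, it is about 5 to 9%, against about 5 to 6% with percentile intervals.

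These sizes assume the protocol's ICC for variables on which it was not measured, path values of 0.3 to 0.8, 122 to 160 dyads with complete data, and a single-mediator simplification. The direction does not depend on the exact values, but the size does. The direct arm effects, including the primary effect on co-rumination, come from the two-level model and are not in question. The change should be made before analysis.

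**What to change.** Replace the bootstrap sentence in Section 10.2 with wording such as: indirect effects in Hypotheses 1 and 5 will be tested with percentile 95% intervals from 10,000 resamples of whole dyads, drawn within arm. If classrooms are in fact the unit randomised under the fallback in Section 8.2, whole classrooms should be drawn for those batches. That passage mentions classroom level but then assigns dyads, so it needs to be made clear. An acceptable alternative is Monte Carlo intervals built from the two-level model's cluster-robust estimates of the two paths.

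The cost is one sentence and a resampling script. Compared with drawing girls, intervals widen by up to about √1.40 = 1.18, or 18%, where the arm path dominates. The percentile interval gives up a little power against the bias-corrected one: in a simulation with a = b = 0.5, 122 dyads and ICC .40, power was 91.0% against 92.0% with dyads resampled.
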